nausea (35%), rash (33%). Grade 3 and 4 drug related events included: low ANC (74%), increased partial thromboplastin time (15%), increased ALT levels (13%), lymphopenia (13%), low platelet numbers (11%), increased lipase levels (5%). Doxorubicin was given 3-weekly in a dose of 60 mg/sqm for a maximum of 6 consecutive cycles for anthracycline naive patients. Sorafenib was given from 100 mg BID to 400 mg BID. Thereby, dose limiting toxicities (DLT) were reported including HFSR and diarrhea. Less frequently observed DLTs were fatigue, hyperuricemia and asthenia. Most of the trials did not reach a maximum tolerated dose. Thus, Sorafenib is well tolerated even in combination treatment approaches.

Myelosuppression was mainly observed after combination therapy with cytotoxic agents and manifested with leukopenia, neutropenia, febrile neutropenia and thrombocytopenia.

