##### 4.1.5.1 Dose modification for hematological toxicity

Hematological toxicities will be considered not relevant for dose modification during the period of chemotherapy and the expected subsequent myelosuppression. However, these criteria will apply after hematopoietic recovery from the last chemotherapy course during the subsequent maintenance therapy.

Toxicity	Grade 1	Grade 2	Grade 3*	Grade 4*
Hematologic	Continue at the same dose level.	Continue at the same dose level.	Withhold dose until toxicity is grade <2, then resume treatment at the same dose level. If patient experiences a second grade 3 toxicity, withhold dose until toxicity is grade <2, then reduce dose to 400 mg p.o. QD and resume treatment.	Withhold dose until toxicity is grade <2, then reduce dose to 400 mg p.o. QD and resume treatment, or discontinue at the discretion of the principal investigator after discussion with study sponsor (safety desk at SAL).

\*Patients who develop grade 3 leukopenia, or grade 3/ grade 4 lymphopenia may continue Sorafenib/ Placebo treatment without interruption at the discretion of the investigator.

Table 3: Dose modifications and delays for hematologic toxicities of Sorafenib/ Placebo

Table 4 summarizes the recommendations for dose delays and modifications for all non-hematologic adverse events, except for skin toxicities and hypertension, which will be detailed separately (Table 5, Table 6, Table 7). These recommendations pertain, if the adverse event is considered to be related to Sorafenib/ Placebo, but not to the chemotherapy.

Toxicity	Grade 1	Grade 2	Grade 3*	Grade 4*
Non-hematologic	Continue at the same dose level.	Continue at the same dose level.	Withhold dose until toxicity is grade <1, then resume treatment at the same dose level. If patient experiences a second grade 3 toxicity, withhold dose until toxicity is grade <1, then reduce dose to 400 mg p.o. QD and resume treatment.	Withhold dose until toxicity is grade <1, then reduce dose to 400 mg p.o. QD. and resume treatment, or discontinue at the discretion of the principal investigator after discussion with study sponsor.

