*Patients who develop grade 3 fever/ chills, grade 3 elevation of hepatic transaminases with ALT and AST <10x ULN, grade 3 hyperlipasemia or hyperamylasemia without clinical or other evidence of pancreatitis may continue Sorafenib/ Placebo treatment without interruption at the discretion of the investigator. Also excludes nausea/ vomiting that has not been premedicated, and diarrhea. If no recovery after 30 day delay, treatment will be discontinued unless patient is deriving clinical benefit. If more than 2 dose reductions are required, treatment will be discontinued.				

*Table 4: Dose modifications for Sorafenib-associated non hematological toxicity except hand-foot skin reactions and hypertension*

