#### 4.1.5.2 Dose modifications for skin toxicity

Only for the purpose of dose delays and modifications, patients experiencing Hand-Foot syndrome should have their signs and symptoms graded according to the following system (see Table 5). Other skin toxicities will be graded according to CTCAE Version 3.0. Please note that Hand Foot Syndrome will be graded and recorded as an adverse event according to CTCAE Version 3.0 in the CRF. These recommendations pertain, if the adverse event is considered to be related to Sorafenib/ Placebo, but not to the chemotherapy.

Grade 1	Numbness, dysesthesia/ paresthesia, tingling, painless swelling or erythema of the hands and/ or feet and/ or discomfort, which does not disrupt normal activities
Grade 2	Painful erythema and swelling of the hands and/ or feet and/or discomfort affecting the patient's activities
Grade 3	Moist desquamation, ulceration, blistering or severe pain of the hands and/or feet and/or severe discomfort that causes the patient to be unable to work or perform activities of daily living.

*Table 5: Grading for Hand-Foot Syndrome*

According to the grade and incidence of skin toxicity (including rash and hand-foot syndrome) for a given patient, the following dose modification schedule will be followed.

Skin toxicity grade	Occurrence	Suggested Dose modification
Grade 1: Numbness, dysethesia, paresthesia, tingling, painless swelling, erythema or discomfort of the hands or feet which does not disrupt the patients normal activity	Any occurrence	Institute supportive measures immediately and continue Sorafenib/Placebo treatment
Grade 2: Painful erythema and swelling of the hands or feet and/or discomfort affecting the patient's normal activities	1 st occurrence	Institute supportive measures and consider a decrease of Sorafenib/Placebo dose to 400mg daily for 28 days If toxicity resolves or returns to grade 0–1 after dose reduction, increase Sorafenib/Placebo to full dose after 28 days If toxicity does not resolve or return to grade 0-1 despite dose reduction, interrupt Sorafenib/Placebo treatment for a minimum of 7 days, until toxicity has resolved or returned to grade 0–1. When resuming treatment after dose interruption, re-start Sorafenib/Placebo at reduced dose of 400mg daily for 28 days If toxicity remains absent or at grade 0–1 at reduced dose, increase Sorafenib/ Placebo to full dose after 28 days

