	2 nd or 3 rd occurrence	Decrease dose to 400mg daily for the study period, do not re-escalate the dose
	4 th occurrence	Decision whether to discontinue Sorafenib/ Placebo treatment should be made based on clinical judgment and patient preference
Grade 3: Moist desquamation, ulceration, blistering or severe pain of the hands or feet, or severe discomfort that causes inability to work or perform activities of daily living	1 st occurrence	Institute supportive measures and interrupt Sorafenib/ Placebo treatment for a minimum of 7 days and until toxicity has resolved or is reduced to grade 0–1 When resuming treatment after dose interruption, re-start Sorafenib/Placebo at reduced dose of 400mg daily for 28 days If toxicity remains absent or at grade 0–1 at reduced dose, increase Sorafenib/ Placebo to full dose after 28 days
	2 nd occurrence	Decrease dose to 400 mg daily for the study period, do not re-escalate the dose
	3 rd occurrence	Decision whether to discontinue Sorafenib/ Placebo treatment should be made based on clinical judgment and patient preference

Table 6: Suggested Dose Modifications for Sorafenib/ Placebo for Hand-Foot Skin Reaction

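### The scope of Table 4 is stated inconsistently, so rash can be read into two dose schedules and grade 3–4 diarrhea has no clear table rule

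*Protocol*

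**What the plan says.** Three statements in Protocol Section 4.1.5.1 set the scope of Table 4.

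- The introducing text says it holds "for all non-hematologic adverse events, except for skin toxicities and hypertension, which will be detailed separately".
- The caption reads "Dose modifications for Sorafenib-associated non hematological toxicity except hand-foot skin reactions and hypertension".
- The footnote marked on both the grade 3 and grade 4 columns first lists events that may continue uninterrupted at the investigator's discretion, and then adds: "Also excludes nausea/ vomiting that has not been premedicated, and diarrhea".

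Two statements in Section 4.1.5.2 set the scope of Table 6.

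- The introducing sentence covers "skin toxicity (including rash and hand-foot syndrome) for a given patient, the following dose modification schedule will be followed".
- The caption reads "Suggested Dose Modifications for Sorafenib/ Placebo for Hand-Foot Skin Reaction".

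The same section separates the grading scales. Hand-foot syndrome is graded by Table 5 for dosing purposes, whereas "Other skin toxicities will be graded according to CTCAE Version 3.0". The grade descriptions in Table 6 refer to hands or feet, and the table stops at grade 3.

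Section 4.1.5, below Table 2, adds a general rule: grade 3 toxicity leads to a permanent reduction, with skin toxicity excepted.

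**The concern.** A site has to know which schedule governs an event before it can act on it. For rash, the introducing texts and the captions point to different tables, and the two tables prescribe different doses at some grades. For diarrhea of grade 3 or 4, the text puts the event inside Table 4 and the footnote appears to take it out, while no other table picks it up.

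These are not rare reactions. Diarrhea (43%) and rash (40%) are the two most frequent events on Sorafenib in Table 19. On the combination with doxorubicin, Section 1.3.2 says: "Thereby, dose limiting toxicities (DLT) were reported including HFSR and diarrhea". At stake are patient safety, uniform exposure in the Sorafenib arm, and a toxicity comparison (a secondary objective in Section 2.3.2) that could pool patients dosed under different rules. Maintenance lasts one year, so a reduction without re-escalation can cover a long period.

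**Working it through.** The plan gives no figure to reproduce here. The check sets the passages side by side and then sizes the groups from the Protocol's own tables.

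**1. Which table governs rash?**

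| Source | Rash belongs to |
|---|---|
| Text introducing Table 4 (4.1.5.1) | not Table 4 |
| Text introducing Table 6 (4.1.5.2) | Table 6 |
| Caption of Table 4 | Table 4 |
| Caption of Table 6 | not Table 6 |

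The two introducing texts agree with each other, and so do the two captions, but the pairs contradict one another.

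**2. Do the actions differ?**

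| Rash | Table 4 | Table 6 | Firm conflict? |
|---|---|---|---|
| Grade 1 | dose unchanged | treatment continues, with supportive measures | no |
| Grade 2, first | dose unchanged | a reduction to 400 mg daily for 28 days is to be considered | no |
| Grade 2, second or third | dose unchanged | 400 mg daily for the study period, no re-escalation | yes |
| Grade 3, first | stop until below grade 1, then the previous dose | stop at least 7 days and until grade 0–1, then 400 mg daily for 28 days | yes |
| Grade 4 | stop, then 400 mg daily, or discontinue | no row | gap in Table 6 |

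For a patient on 800 mg daily, the 28-day step after a first grade 3 rash delivers 28 × 400 = 11,200 mg, against 28 × 800 = 22,400 mg if the same dose is resumed. After a second grade 2 rash, Table 6 keeps the patient at half the daily dose that Table 4 would leave unchanged.

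**3. Which rule covers grade 3–4 diarrhea?**

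- Table 3 is hematologic, Tables 5 and 6 concern skin and hand-foot reactions, and Table 7 concerns hypertension. None covers diarrhea.
- Footnote read as an exclusion: Table 4 does not cover it either, so no dose table gives an action.
- Footnote read as extending the list just before it: diarrhea may continue at the investigator's discretion, at grade 4 as well as grade 3.
- It is also unclear whether the premedication qualifier attached to nausea and vomiting extends to diarrhea.
- The general rule in Section 4.1.5 reaches grade 3 diarrhea by its wording. It states no withholding step and does not mention grade 4. It also disagrees with Table 4, which returns the patient to the same dose after a first grade 3 event.

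**4. How many patients?** Inputs: 138 patients per arm (Section 7.1) and the Sorafenib columns of Tables 19 and 20. Formula: rate × 138.

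| Event | Table 19 | Table 20 |
|---|---|---|
| Rash, any grade | 0.40 × 138 = 55 | 0.19 × 138 = 26 |
| Rash, grade 3 | <1%, fewer than 1.4 | 0.01 × 138 = 1.4 |
| Diarrhea, grade 3 | 0.02 × 138 = 3 | 0.10 × 138 = 14 |

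Neither table gives a separate rate for grade 2 or for repeat rash. Grade 4 rash is 0% in both. Grade 4 diarrhea is 0% in Table 19 and <1% in Table 20.

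**The case against.** The best defense on rash is that the operative text is consistent. Section 4.1.5.1 removes skin toxicity from Table 4, Section 4.1.5.2 is headed for skin toxicity and names rash, the first column of Table 6 is headed by skin toxicity grade, and the general rule sets skin apart. Against that stand two loose captions. A reader could also apply the Table 6 rows by CTCAE grade number and ignore the hand and foot descriptions. This largely stands: the body text favors Table 6. A reader might infer that sites will dose the same rash differently, but the Protocol supports only that they can.

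On diarrhea, a reader might infer that grade 3–4 events have no rule at all. That is too strong. The general rule reaches grade 3, Section 3.4 requires withdrawal for unacceptable toxicity, and the footnote has a discretionary reading. None of these settles the matter. The general rule conflicts with Table 4, Section 3.4 sets no threshold, and the footnote does not say which reading is meant.

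On size, the 55 or 26 patients should not be taken as the number affected. They include grade 1 rash, where the tables do not conflict, and first grade 2 rash, where Table 6 only asks that a reduction be considered. The rates are treatment-emergent (rash was 16% and 14% on placebo), whereas Tables 4 and 6 apply only to events attributed to study drug.

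Finally, the same rules apply to Sorafenib and placebo tablets under double-blinding. Divergent readings add variability in exposure, but nothing in the Protocol shows that they favor an arm or shift EFS.

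**Conclusion.** The contradiction is real and should be corrected, but its reach is narrower than the any-grade counts suggest. For rash, the firm divergence is confined to repeat grade 2 and first grade 3 events, plus the missing grade 4 row. Grade 3 rash would be about one patient in 138 or fewer. Most of the exposure to the conflict would therefore come from repeat grade 2 rash, whose rate the Protocol does not give and which can only be bounded above by 55 or 26.

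For diarrhea, about 3 or 14 of 138 Sorafenib patients could have a grade 3 event for which the footnote, the introducing text and the general rule do not yield one instruction. All counts assume that rates from the renal and hepatocellular trials carry over to AML patients receiving chemotherapy. The conclusion that the passages disagree does not depend on that assumption.

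**What to change.** Reconcile Sections 4.1.5, 4.1.5.1 and 4.1.5.2.

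- State the scope of Table 4 once and repeat it identically in the introducing text, the caption and the footnote.
- Name the one table that governs rash. If it is Table 6, give it a title that includes rash and grade rows that fit CTCAE-graded skin toxicity, including grade 4. If it is Table 4, change both introducing texts.
- Reword the footnote so that grade 3 and grade 4 diarrhea each have one identifiable rule, and make clear what the premedication qualifier covers.
- Bring the general rule on grade 3 toxicity and the first-event instruction in Table 4 into agreement.

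Which clinical action applies in each case is for the sponsor to decide. The cost is amendment wording for one paragraph in each of the three sections and for two tables, with no additional patients, visits or data.

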#### 4.1.5.2 Dose modifications for skin toxicity

Only for the purpose of dose delays and modifications, patients experiencing Hand-Foot syndrome should have their signs and symptoms graded according to the following system (see Table 5). Other skin toxicities will be graded according to CTCAE Version 3.0. Please note that Hand Foot Syndrome will be graded and recorded as an adverse event according to CTCAE Version 3.0 in the CRF. These recommendations pertain, if the adverse event is considered to be related to Sorafenib/ Placebo, but not to the chemotherapy.

Grade 1	Numbness, dysesthesia/ paresthesia, tingling, painless swelling or erythema of the hands and/ or feet and/ or discomfort, which does not disrupt normal activities
Grade 2	Painful erythema and swelling of the hands and/ or feet and/or discomfort affecting the patient's activities
Grade 3	Moist desquamation, ulceration, blistering or severe pain of the hands and/or feet and/or severe discomfort that causes the patient to be unable to work or perform activities of daily living.

*Table 5: Grading for Hand-Foot Syndrome*

According to the grade and incidence of skin toxicity (including rash and hand-foot syndrome) for a given patient, the following dose modification schedule will be followed.

Skin toxicity grade	Occurrence	Suggested Dose modification
Grade 1: Numbness, dysethesia, paresthesia, tingling, painless swelling, erythema or discomfort of the hands or feet which does not disrupt the patients normal activity	Any occurrence	Institute supportive measures immediately and continue Sorafenib/Placebo treatment
Grade 2: Painful erythema and swelling of the hands or feet and/or discomfort affecting the patient's normal activities	1 st occurrence	Institute supportive measures and consider a decrease of Sorafenib/Placebo dose to 400mg daily for 28 days If toxicity resolves or returns to grade 0–1 after dose reduction, increase Sorafenib/Placebo to full dose after 28 days If toxicity does not resolve or return to grade 0-1 despite dose reduction, interrupt Sorafenib/Placebo treatment for a minimum of 7 days, until toxicity has resolved or returned to grade 0–1. When resuming treatment after dose interruption, re-start Sorafenib/Placebo at reduced dose of 400mg daily for 28 days If toxicity remains absent or at grade 0–1 at reduced dose, increase Sorafenib/ Placebo to full dose after 28 days
	2 nd or 3 rd occurrence	Decrease dose to 400mg daily for the study period, do not re-escalate the dose
	4 th occurrence	Decision whether to discontinue Sorafenib/ Placebo treatment should be made based on clinical judgment and patient preference
Grade 3: Moist desquamation, ulceration, blistering or severe pain of the hands or feet, or severe discomfort that causes inability to work or perform activities of daily living	1 st occurrence	Institute supportive measures and interrupt Sorafenib/ Placebo treatment for a minimum of 7 days and until toxicity has resolved or is reduced to grade 0–1 When resuming treatment after dose interruption, re-start Sorafenib/Placebo at reduced dose of 400mg daily for 28 days If toxicity remains absent or at grade 0–1 at reduced dose, increase Sorafenib/ Placebo to full dose after 28 days
	2 nd occurrence	Decrease dose to 400 mg daily for the study period, do not re-escalate the dose
	3 rd occurrence	Decision whether to discontinue Sorafenib/ Placebo treatment should be made based on clinical judgment and patient preference

Table 6: Suggested Dose Modifications for Sorafenib/ Placebo for Hand-Foot Skin Reaction

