#### 4.1.5 Dose modification and delays of Sorafenib or Placebo

The modifications of Sorafenib or Placebo will follow the following pre-defined dose levels:

Dose level 1 (starting dose):	400 mg BID (2 tablets twice a day)
Dose level 2:	400 mg QD (2 tablets once a day)
Dose level 3:	400 mg QOD (2 tablets every second day)

Table 2: Sorafenib dose levels

Please note that the dose of 400 mg BID (total daily dose 800 mg) is the standard dose. If a dose reduction below 400 mg QOD (2 tablets every other day) is required, the patient should be discontinued from the study treatment. After resolution of the adverse event, the dose may be re-escalated from dose level 2 or 3 to the starting dose (see table) at the discretion of the investigator. As a general rule, grade 3 toxicity should be followed by permanent dose reduction. Exceptions are skin toxicities as defined below.

Resolution of an adverse event is defined as disappearance or reduction of the adverse event to below grade 3 toxicity. For patients with toxicities  $\geq$  grade 2 present at baseline (before start of Sorafenib/ Placebo treatment), resolution to maximum grade 1 level will apply.

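### Table 6 states no interruption and no recovery grade at a second grade 3 skin reaction, although it states both at the first

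*Protocol*

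**What the plan says.** Section 4.1.5.2 of the protocol introduces Table 6 by saying that, according to grade and incidence of skin toxicity, "the following dose modification schedule will be followed". The column heading and the caption call the modifications suggested.

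The grade 3 rows (moist desquamation, ulceration, blistering, severe pain or disabling discomfort) read as follows.

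- **First occurrence:** "Institute supportive measures and interrupt Sorafenib/ Placebo treatment for a minimum of 7 days and until toxicity has resolved" or has fallen to grade 0-1. Restart is at 400 mg daily for 28 days, then at full dose if the reaction stays at grade 0-1.
- **Second occurrence:** "Decrease dose to 400mg daily for the study period, do not re-escalate the dose". Nothing else is stated. The same instruction, differing only in spacing, serves the second or third grade 2 reaction.
- **Third occurrence:** whether to discontinue is left to clinical judgment and patient preference, with no word on dosing in the meantime.

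For a first grade 2 reaction, once the dose has been cut to 400 mg daily, the table says: "If toxicity does not resolve or return to grade 0-1 despite dose reduction, interrupt Sorafenib/Placebo treatment for a minimum of 7 days".

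The other toxicity tables do not cover skin. Section 4.1.5.1 states: "Table 4 summarizes the recommendations for dose delays and modifications for all non-hematologic adverse events, except for skin toxicities and hypertension". Section 4.1.5 also exempts skin toxicity from its general rule of permanent reduction after grade 3 toxicity.

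**The concern.** The schedule becomes less explicit, and on its face less protective, as the reaction recurs. A first grade 3 reaction brings a defined hold with a minimum length and a recovery grade. A recurrence brings only a dose cut. A milder reaction, a first grade 2 that persists on 400 mg daily, is interrupted, while a new grade 3 reaction on that same dose has no stated interruption.

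Two things are at stake. One is safety in patients with recurrent ulceration or blistering. The other is uniform handling across centers: a site that carries the first-row hold forward will stop the drug, and a site that reads the second cell literally need not. The efficacy analysis is not at stake.

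**Working it through.** No figure in the plan depends on this rule, so the main check compares the cells.

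**1. The cells side by side**

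| Situation | Hold stated | Recovery grade | Dose afterwards |
|---|---|---|---|
| Table 6, grade 2, first, persisting on 400 mg daily | at least 7 days | 0-1 | 400 mg daily for 28 days, then full |
| Table 6, grade 3, first | at least 7 days | 0-1 | 400 mg daily for 28 days, then full |
| Table 6, grade 3, second | none | none | 400 mg daily, permanent |
| Table 6, grade 3, third | none | none | decision on discontinuation |

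**2. Does the second-occurrence cell always change the dose?** No. A patient can already be on 400 mg daily in two ways: in the 28-day step-down after a first grade 3 reaction (or a first grade 2 reaction), or fixed there after a second grade 2 reaction. In both cases the current dose stays the same. In the step-down case the cell only makes the reduction permanent.

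**3. Does other text supply the hold?** It permits one but does not require one.
- Table 4 excludes skin, and section 4.1.5 exempts it.
- Section 6.3.1.2 says management of skin toxicity may include temporary interruption, without tying this to grade or occurrence.
- Section 3.4 deals with withdrawal, not with a temporary hold.

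**4. How many patients?** Inputs:
- 138 per arm (section 7.1).
- Grade 3 hand-foot rates of 6% (Table 19, renal cancer) and 8% (Table 20, liver cancer).
- Remission in 70-80% (section 1.1) and transplantation in about 10% of all patients (section 7.1).
- Recurrence after a first grade 3 event: not given in the protocol, assumed 25-50%.

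Counting only patients who go on to consolidation with study drug:
- 138 × (0.70 − 0.10) = 82.8 and 138 × (0.80 − 0.10) = 96.6 patients.
- First grade 3 events: 82.8 × 0.06 = 5.0 and 96.6 × 0.08 = 7.7.
- Recurrences: 5.0 × 0.25 = 1.2 and 7.7 × 0.50 = 3.9.

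Counting all 138, since study drug starts on day 10 of induction:
- 138 × 0.06 × 0.25 = 2.1 and 138 × 0.08 × 0.50 = 5.5.

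Together this is roughly 1 to 6 patients, or 1.2/138 = 0.9% to 5.5/138 = 4.0%. If recurrence were 10%, the same steps give 0.5 to 0.8 patients (consolidation only) or 0.8 to 1.1 (all 138).

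**5. When does it matter most?** Planned drug-free gaps cover some cases.
- Between inductions: days 20-21 plus days 1-9 of the next course = 2 + 9 = 11 days at least.
- Between consolidations: 2 to 3 days plus days 1-7 = 9 to 10 days.

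Both exceed 7 days, although neither is tied to recovery to grade 0-1. Maintenance runs continuously for a year with no planned gap, so the cell matters mainly there.

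**The case against.** The best case for leaving the table alone has four parts.

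**The cell is silent, not permissive.** Where Table 6 means uninterrupted dosing, as at grade 1, it says so. The ban on re-escalation answers the last step of the first-occurrence cell, so the second cell can be read as changing only what follows recovery. It also omits supportive measures, and no site would stop those. This stands. A reader might infer that the protocol orders drug to continue through recurrent ulceration; the text does not say that. But the second cell tells the investigator to decrease the dose, which naturally describes a patient who keeps taking drug, and the hold is spelled out in two other cells of the same table. The ambiguity is real.

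**Discretion already covers it.** The table is headed as suggested, section 6.3.1.2 allows interruption or discontinuation, section 3.4 requires withdrawal for unacceptable toxicity, and the lower dose levels in section 4.1.5, including 400 mg every other day, remain open. This stands, and it is why the point is minor. It does not explain why a hold is prescribed at the first event and left to discretion at the second.

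**Skin has its own scheme.** Tables 3 and 4 both withhold drug at a second grade 3 toxicity (Table 4: "If patient experiences a second grade 3 toxicity, withhold dose until toxicity is grade <1, then reduce dose to 400 mg p.o. QD"). A reader might infer that Table 6 contradicts them. It does not: skin toxicity is expressly carved out of Table 4, Table 3 is hematologic, and the footnotes of both let some grade 3 events continue without interruption. They show a different approach and no more. The unevenness within Table 6 stands without them.

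**Other cells are equally silent.** The third grade 3 cell and the later grade 2 cells also name no hold. For the third grade 3 cell this is a fair criticism, and the fix covers it. The later grade 2 cells concern a milder reaction, for which even the first-occurrence rule interrupts only if a dose cut has failed.

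**Conclusion.** The point holds as a gap in one row of a safety table. At a second grade 3 skin reaction Table 6 requires no interruption and sets no recovery grade, and for a patient already on 400 mg daily it leaves the current dose as it is. A hold is permitted everywhere and required nowhere.

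The count of about 1 to 6 of 138 rests on an assumed recurrence rate and on hand-foot rates from trials in renal and liver cancer. It is tempting to read such a figure as a ceiling, but the protocol does not support one. Table 6 also covers rash, which the count leaves out, and the lower end omits patients treated only in induction. In the other direction, planned drug-free gaps remove some cases, and a 10% recurrence rate would leave about one patient or fewer. Nor does the protocol allow a count of the recurrences that fall on 400 mg daily.

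Sample size, power, type I error and the primary analysis are untouched. Severity is minor; the change is a cheap improvement.

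**What to change.** Amend two cells of Table 6.

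- **Grade 3, second occurrence:** start supportive measures; interrupt Sorafenib/Placebo for at least 7 days and until the reaction has resolved or is at grade 0-1; then resume at 400 mg daily for the rest of the study, without re-escalation.
- **Grade 3, third occurrence:** add that study drug is interrupted while discontinuation is being decided.

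The cost is a table amendment, with no extra visits or patients. The downside is slightly less drug exposure in a few patients, and possible withdrawal under section 3.4 if a hold exceeds 28 consecutive days. After the 7-day minimum, 28 − 7 = 21 days remain for recovery, and the first-occurrence row already carries that risk.
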